#### 4.4.1 Informed Consent/Assent

The investigational nature and objectives of the trial, the procedures and treatments involved and their attendant risks and discomforts, and potential alternative therapies will be carefully explained to the patient or the patient's parents or guardian if the patient is a child. All patients and/or their parents or legally authorized representatives must sign a written informed consent. Assent, when appropriate, will be obtained according to institutional guidelines

## 4.4.2 Screening Procedures

Diagnostic or laboratory studies performed exclusively to determine eligibility for this trial must only be done after obtaining written informed consent. Documentation of the informed consent for screening will be maintained in the patient's research chart. Studies or procedures that were performed for clinical indications (not exclusively to determine eligibility) may be used for baseline values even if the studies were done before informed consent was obtained.

## 4.4.3 Eligibility Checklist

Before the patient can be enrolled, the responsible institutional investigator must sign and date the completed eligibility checklist. A signed copy of the checklist will be uploaded into RAVE immediately following enrollment.

## 4.4.4 Institutional Pathology Report

Immediately following enrollment, the institutional pathology report for the diagnosis under which the patient is being enrolled must be uploaded into RAVE. The report must include the associated study number and COG patient registration and accession numbers. Personal identifiers, including the patient's name and initials must be removed from the institutional pathology report prior to submission.

## 5 BIOMARKER, CORRELATIVE, AND SPECIAL STUDIES

## Table 2: List of Biomarkers in Order of Priority

*Note for participating sites*: See Table 3 for details on specimens to collect. The specimens tested are not always the same specimens that are submitted by the site, as processing of blood and tissue will occur at the EET Biobank prior to testing.

Priority	Biomarker Name	Assay (CLIA: Y/N)	Use in the Trial (Integral, Integrated, or Exploratory) AND Purpose	Specimens Tested	Collection Time Points		Assay Laboratory and Lab PI
Tissue-k	oased Biomarl	kers					l
1	MIBI for immune cell infiltration	Multiple xed ion beam imaging CLIA: N No Review Require d	Exploratory  1) Understand the baseline immune cell infiltration in archival samples of relapsed or refractory neuroblastoma and osteosarcoma  2) Compare the immune cell infiltration before and after treatment with anti-CD47/anti-GD2 in patients with relapsed pulmonary osteosarcoma undergoing staged resections  3) Compare the immune cell infiltration before and after treatment with anti-CD47/anti-GD2 in patients with relapsed osteosarcoma or neuroblastoma undergoing optional	FFPE tumor tissue	1) Archival Tissue  2) Pulmonary Metastases resected from staged resection at enrollment and then after one cycle of protocol therapy (cohort B4 only)  3) Clinical biopsies obtained during therapy or at disease progression	Mandatory (cohort B4	[name] Laboratory, Department of Pathology, Stanford University [name] [contact]

This protocol is for research purposes only, see page 1 for usage policy

Priority	Biomarker Name	Assay (CLIA: Y/N)	Use in the Trial (Integral, Integrated, or Exploratory) AND Purpose	Specimens Tested	Collection Time Points		Assay Laboratory and Lab PI
2	CD47 Expression	Immuno histoche mistry CLIA: N No Review Require d	Exploratory Assess contribution of CD47 to disease response	Unstained slides from FFPE tumor tissue	1) Archival Tissue  2) Pulmonary Metastases resected from staged resection at enrollment and then after one cycle of protocol therapy (cohort B4 only)  3) Clinical biopsies obtained during therapy or at relapse	Optional	Stanford Pathology
3	Sample Banking		Sample banking for future study	Frozen tumor tissue (when available)	1) Available archival tissue  2) Pulmonary Metastases resected from staged resection at enrollment and then after one cycle of protocol therapy (cohort B4 only)  3) Clinical biopsies obtained during therapy or at disease progression	Optional	EET Biobank

Priority	Biomarker Name	Assay (CLIA: Y/N)	Use in the Trial (Integral, Integrated, or Exploratory) AND Purpose	Specimens Tested	Collection Time Points	Mandatory or Optional	Assay Laboratory and Lab PI
4	CyTOF for immune subsets	Mass Cytomet ry CLIA: N	Exploratory  To determine changes in the peripheral immune subsets as a result of treatment with anti-CD47 / anti-GD2	marrow in	1) Baseline 2) Disease restaging (cycle 2, 4, 8, 12) 3) End of therapy	1) Nandatory (fresh or viably frozen) 2) Nandatory 3) Coptional	.edu
5	Sample Banking		Sample banking for future study	Mononucle arcells and plasma from bone marrow in Sodium Heparin and EDTA tubes (Bilateral)	Baseline if available  Disease restaging (cycle 2, 4, 8, 12)  End of therapy	Optional	EET Biobank
Blood-b	ased Biomark	ers		•			
1	Magrolimab PK	ELISA CLIA: N No Review Require d	Integrated Assess the drug concentrations achieved during this first in child trial	Serum from Red top tube	Safety lead-in D1, 8, 15 Cycle 1, D1, 8, 15, ARM B only: D22 Cycle 2, D1 Cycle 3, D1 Cycle 5, D1 Cycle 7, D1 Cycle 9, D1 Cycle 11, D1 End of therapy (all samples drawn prior to magrolimab infusion)	M (safety cohort and first three patients on any expansion cohorts)	PPD

Version Date: 02/02/2024

Priority	Biomarker Name	Assay (CLIA: Y/N)	Use in the Trial (Integral, Integrated, or Exploratory) AND Purpose	Specimens Tested	Collection Time Points	Mandatory or Optional	Assay Laboratory and Lab PI
2	Magrolimab anti-drug antibody (ADA) Testing	ECLIA CLIA: N No Review Require d	Integrated Assess for immune responses against magrolimab	Serum from Red top tube	Safety lead-in D1  Cycle 1, D1  Cycle 2, D1  Cycle 3, D1  Cycle 5, D1  Cycle 7, D1  Cycle 9, D1  Cycle 11, D1  End of therapy  (all samples drawn prior to magrolimab infusion)	M (safety cohort and first three patients on any expansion cohorts)	PPD
3	FcR receptor polymorphis m	RT-PCR CLIA: N No Review Require d	Exploratory Assess contribution of FcR polymorphisms to disease response	PBMC from EDTA tube	Baseline: Arm A: Safety Lead In-Week 1, D1 Arm B: Cycle 1, D1	Optional	[name] Laboratory, University of Wisconsin) [name] [name]
4	KiR phenotyping	RT-PCR CLIA: N No Review Require d	Exploratory Assess contribution of KiR mismatching to disease response	PBMC from EDTA tube	Baseline: Arm A: Safety Lead In-Week 1, D1 Arm B: Cycle 1, D1	Optional	[name] Laboratory, University of Wisconsin [name] [name]

Priority	Biomarker Name	Assay (CLIA: Y/N)	Use in the Trial (Integral, Integrated, or Exploratory) AND Purpose		Collection Time Points	Mandatory or Optional	Assay Laboratory and Lab PI
5	HACA antibody testing	ELISA CLIA: N No Review Require d	Exploratory  Assess contribution of Human anti- chimeric antibody response to disease response		ARM A: Cycle 1: Day 1, 5  ARM B: Cycle 1: Day 8, 12  Cycle 2: Day 1 and 5  Cycle 4: Day 1 and 5  End of therapy	Mandatory	[name] Laboratory, University of Wisconsin [name] [name]
6	Luminex for peripheral cytokines	Lumine x CLIA: N No Review Require d	Exploratory  To assess for the presence of human cytokines	In HIII A	Safety Lead-In and Cycles 1-2: Weekly prior to magrolimab infusion  Subsequent cycles: Day 1 prior to infusion  End of therapy	Mandatory	Stanford Human Immune Monitoring Center (HIMC) [name] [name]
7	CyTOF for peripheral immune subsets	Mass Cytomet ry CLIA: N No Review Require d	Exploratory  To determine changes in the peripheral immune subsets as a result of treatment with anti-CD47/anti-GD2	in Sodium	Safety Lead-In and Cycles 1-2: Weekly prior to magrolimab infusion  Subsequent cycles: Day 1  End of therapy	Mandatory	Stanford Cancer Correlative Science Unit (CCSU) [name] [name]

This protocol is for research purposes only, see page 1 for usage policy

Priority	Biomarker Name	Assay (CLIA: Y/N)	(Integral,	the Trial Integrated, ratory) AND	Tested	Collection Time Points	v	Assay Laboratory and Lab PI
8	Sample Banking		Sample ba future stud	_	PBMCs from blood in EDTA	cycles 1-2: Weekly prior to magrolimab	Mandatory (bank cells when plasma is collected for cytokines)	EET Biobank

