## 2.3 Correlative Studies Background

**2.3.1** Explore biomarkers of response and resistance including genomic (CD47 expression, FcR polymorphisms and KiR phenotype) and immunologic (dinutuximab HACA, magrolimab ADA, peripheral immune subsets, and circulating cytokines)

CD47 expression is ubiquitous on most human tissues. It is currently unknown whether expression (qualitative or

quantitative) of CD47 on tumor cells or surrounding cells in the tumor microenvironment is predictive of response to CD47 blockade. CD47 expression will be assessed by immunohistochemistry using a validated antibody on tumor tissue, where available, including archival samples, tumor biopsy samples, and bone marrow samples (when involved by disease).

Genetic polymorphisms in the Fc Receptor (FcR) and Killer Cell Immunoglobulin-Like Receptor (KIR) phenotype have been associated with variable responses to antibody-based therapies, including anti-GD2 in neuroblastoma (Erbe et al., 2018; Siebert et al., 2016). Macrophage activity (as well as NK cell activity) are targets of anti-CD47 therapy, and these receptors may make a patient more or less likely to respond to anti-CD47 and/or anti-GD2.

As dinutuximab is a chimeric antibody consisting of murine variable regions fused to a human Fc region, some patients develop antibodies capable of recognizing and neutralizing dinutuximab (human anti-chimera antibodies, HACA). It is expected that many neuroblastoma patients on this trial will have been previously treated with dinutuximab. We will therefore measure baseline and on-treatment HACA as has been previously reported in the literature ([name] et al., 2014).

Anti-CD47 can unleash the innate immune system through activation of macrophages and NK cells, but has also been shown to generate/unleash a native T cell response (Tseng et al., 2013). Therefore, patient blood and bone marrow (when obtained for disease evaluation) will be subjected to immune phenotyping to look for immune activation/response using validated CyTOF panels. Additionally, patient plasma will be collected during therapy to look for changes in circulating cytokines using the Luminex platform.

**2.3.2** Explore biomarkers of response in the tumor microenvironment through MIBI on resected tissue or archival tissues including comparison of pre- and post- treatment tumor tissues from patients undergoing staged resection of pulmonary osteosarcoma

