### • Processing of Blood and Bone marrow

Upon receipt at the EET Biobank, fresh bone marrow in EDTA tubes and sodium heparin tubes as well as blood in EDTA tubes, sodium heparin tubes will be processed for mononuclear cells and plasma. Cells will be stored at  $5 \times 10^6$  cells per vial in freezing media. At C1D1, 2 mL of blood in EDTA (of the 6 mL blood in EDTA received) will be extracted for DNA.

Frozen serum will be accessioned and stored as listed below.

Viably frozen bone marrow, processed locally per institutional SOPs, for mononuclear cells and plasma, will be accessioned and stored as listed below.

Processed samples will be stored at the EET Biobank as outlined below until they are ready to be sent for analyses as defined in the protocol.

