Dinutuxima b	Administration requires premedication (acetaminophen - oral, diphenydramine -IV, and analgesia) and hydration prior to initiation according	650 mg) of acetaminophen ; 0.5 - 1 mg/ kg (max 50 mg) of	PO Diphenhydramin e^ IV (no need to	Cycles 1 (Week 2): Days 2-5  Subsequent cycles: Days	

to Section 6.2.1.4	ne^	immediate	2-5 of the first
		follows previous	week of each
	Analgesia per	drug infusion)	subsequent
	section 6.2.1.4		cycle
		Analgesia as	
	_	described below	
	$17.5 \text{ mg/m}^2$	in Section	
		6.2.1.4 .	
Administer 0.9% Sodium Chloride Injection USP 10 mL/kg as an IV over 1 hour prior to initiating drug infusion		Dinutuximab in 100 mL bag of 0.9% Sodium Chloride Injection USP (mix by gentle inversion- DO NOT shake)	

\* Determined during dose finding cohort.

Table 7: Regimen Description for Arm B - Expansion Cohort B4 Staged Resection - Post Resection with Delayed Restart > 4 weeks (Resectable, pulmonary only relapsed osteosarcoma\*\*)

**Post-Surgical** resection for staged bilateral pulmonary metastases (regimen for at least 1 cycle prior to pulmonary metastesectomy) if restart delayed

Agent	Premedications; Precautions	Dose	Route	Schedule	Cycle Length
Hu5F9-G4 (magrolima b)	Administer according to guidelines in Section 6.2.1.3. Acetaminophen	650 mg) of acetaminophen; 0.5 - 1 mg/ kg (max 50 mg) of diphenhydramine^	n PO; Diphenhydrami ne IV  Priming: Infuse IV (peripheral	Post resection Priming: Day 1, Week 1	21 days (3 weeks)
	reactions during and for 1-hour post infusion during the priming dose. Any patients experience AEs during this period should be monitored as clinically indicates for up to 24 hours post infusion. Treatment of infusion reactions will be	Cycles 1-2: Hu5F9-G4 (magrolimab) RP2D mg/kg*	infusions:	Post resection Cycle 1: Day 1, Weeks 2, 3 and 4  Post resection Cycle 2: Day 1 of each week	

\*\* Cycles may be repeated as long as the patient does not have unacceptable toxicity (see **Section 6.3** or **Section** Error! Reference source not found.) or disease progression to a maximum of 12 cycles (in Cohorts B1 through B3) or to a maximum of 5 cycles post resection (Cohort B4)

^ Hydroxyzine (0.5-1 mg/kg, Max dose 50 mg) PO may substitute for diphenhydramine

	according to standard operating procedures.			Post resection Cycle 3 and subsequent cycles: Day 1 of Weeks 1 and 3 of each cycle (Week 2 is skipped)	

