Correlative Exploratory Biol	logy Studies										
Tumor tissue specimen 	X	X - As available									
Blood samples 		X	X	X	X	X	X	X	X		
Bone marrow aspirate 	X	→	→ End of Cycle 2, 4, 8 and 12					8 and 12	X		

Arm B patients will receive the priming dose followed by Cycle 1 and 2 (each 21 days). Cycles may be repeated as long as the patient does not have unacceptable toxicity (see Section 6.3 or Section Error! Reference source not found.) or disease progression to a maximum of 12 cycles for patients in cohorts B1, B2 and B3 and to a maximum of 5 cycles post resection for patients in cohort B4.

Standard medical history is acceptable. Following screening, updates to medical history should be recorded.

Prior and concomitant medications – All medications taken within 21 days prior to treatment initiation and all new medications, including all medications for AEs, taken up to 30 days after treatment discontinuation should be recorded.

Hu5F9-G4 (magrolimab) will be administered as a priming dose, single agent Safety Lead-In and Day 1 of every week of every 3 week Cycles as outlined in Section 6.2. A premedication regimen (oral acetaminophen and diphenhydramine, or comparable regimen) is required before the initial doses of Hu5F9-G4 (magrolimab) and in case of re-priming of the patient after > 4 weeks interruption in treatment.

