# APPENDIX O: HUMAN ANTI-CHIMERA ANTIBODIES (HACA) TESTING WORKSHEET FOR ARM B

COG Pt ID # Please do not write pat	ient names on this form o	or on samples.		
Patient Weight: Hu5F9-G4 (Magrolin Dinutuximab Dose:	mab) Dose:		al Daily Dose: al Daily Dose:	mg IV infusion mg IV infusion
_		ing patients in red top tubes at the timepoi	nts listed in Section 5	5.0 .
Record the exact date  Blood Sample  No.	Time Point	Scheduled Collection Time	Actual Date Sample Collected	Actual Time Sample Collected (24-hr clock)
1	Cycle 1, Day 8	Prior to dinutuximab infusion	/ /	
2	Cycle 1, Day 12	Immediately after dinutuximab infusion	//	_ _ :
Blood Sample No.	Time Point	Scheduled Collection Time	Actual Date Sample Collected	Actual Time Sample Collected (24-hr clock)
3	Cycle 2, Day 1	Prior to dinutuximab infusion	/ /	
4	Cycle 2, Day 5	Immediately after dinutuximab infusion		
Blood Sample No.	Time Point	Scheduled Collection Time	Actual Date Sample Collected	Actual Time Sample Collected (24-hr clock)
5	Cycle 4, Day 1	Prior to dinutuximab infusion	/ /	
6	Cycle 4, Day 5	Immediately after dinutuximab infusion	//	_ _ :
Blood Sample No.	Time Point	Scheduled Collection Time	Actual Date Sample Collected	Actual Time Sample Collected (24-hr clock)
7	End of Therapy		/ /	
Section 5.0, in additi	on to detailed guidelin	ploaded into RAVE. A second copy shoul es for packaging and shipping samples.		•
if this form will be u	sed as a source docum	ent, the site personnel who collected the sa	amples must sign and	date this form below:
Signature:(site personnel respo	nsible for collection of	samples)	Date:_	

COG Pt ID#

THIS PROTOCOL IS FOR RESEARCH PURPOSES ONLY, SEE PAGE 1 FOR USAGE POLICY

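### Arm B Cycle 1 sampling labels follow two different day counts, and one of them puts the pre-dinutuximab HACA draw after the first dinutuximab course

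*Combined protocol and SAP*

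**What the plan says.** **HACA schedule.** Table 2 makes HACA mandatory and sets the Cycle 1 samples at "ARM A: Cycle 1: Day 1, 5" and "ARM B: Cycle 1: Day 8, 12". In the Arm B worksheet (Appendix O), the Cycle 1 Day 8 sample carries the instruction "Prior to dinutuximab infusion", and the Day 12 sample is to be drawn straight after the infusion. The remaining Arm B time points are in Cycles 2 and 4 and at end of therapy. Section 2.3.1 expects many neuroblastoma patients to have had dinutuximab before and concludes: "We will therefore measure baseline and on-treatment HACA".

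**Places that start Cycle 1 after a separate priming week.**
- Table 6 puts priming in Week 1 and Cycle 1 magrolimab in Weeks 2 to 4, with dinutuximab at "Cycles 1 (Week 2): Days 2-5".
- The Arm B calendar in Section 11 gives priming its own column, and footnote 1 reads "Arm B patients will receive the priming dose followed by Cycle 1 and 2 (each 21 days".
- The Arm B Luminex, CyTOF and banking worksheets (Appendices Q, S and U) list Priming Day 1, then Cycle 1 Days 1, 8 and 15.

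**Places that fit only a count from priming.**
- The HACA row of Table 2, and Appendix O.
- The PK row of Table 2: "Cycle 1, D1, 8, 15, ARM B only: D22 Cycle 2, D1".
- The FcR and KiR rows of Table 2, which pair the Arm A priming draw with Arm B Cycle 1 Day 1.
- Section 5.2: "At C1D1, 2 mL of blood in EDTA (of the 6 mL blood in EDTA received) will be extracted for DNA". For Arm B, Table 3 lists 2 mL plus 4 mL of EDTA blood only at priming. Later draws are 4 mL.
- Section 8.1.1, which places the priming dose on Cycle 1 Day 1.
- Footnote 13 of the Arm B calendar, which treats C1D1 as the start of treatment.

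**The concern.** One label, Cycle 1 Day 8, means two different dates for the same patient. On the Luminex or CyTOF sheet it is the start of Week 3. On the HACA sheet it makes sense only as the start of Week 2. A coordinator who carries the Table 6 count over to the HACA sheet would take the sample meant to precede dinutuximab after the whole first course.

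At stake is the baseline that Section 2.3.1 asks for. Prior GD2 antibody is allowed (Section 3.1.4), so antibody present at entry has to be told apart from antibody raised on study. Only a sample taken before the first on-study infusion does that, and no other scheduled Arm B HACA draw falls before dinutuximab. Table 3 calls for HACA serum, and the two serum tubes at Arm B priming go to the PK/ADA laboratory. A missed baseline cannot be redrawn.

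**Working it through.** **Inputs.** Priming is Week 1 Day 1, taken as study day 1. The first dinutuximab course is Week 2 Days 2–5 (Table 6). Cycle 1 lasts 21 days (Arm B calendar, footnote 1). Cohort sizes are from Section 9.3.3.

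**Formulas.** Study day of week w, day d = 7 × (w − 1) + d. Dinutuximab is therefore given on study days 7 + 2 = 9 to 7 + 5 = 12. A label Cycle 1 Day k is study day 7 + k under Table 6, and study day k if counted from priming.

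| Cycle 1 label | Table 6 count | Count from priming |
|---|---|---|
| Day 1 | study day 8 (Week 2 Day 1), before dinutuximab | study day 1, the priming dose |
| Day 5 | study day 12 (Week 2 Day 5), last infusion day | study day 5, before dinutuximab |
| Day 8 | study day 15 (Week 3 Day 1), after the course | study day 8 (Week 2 Day 1), before dinutuximab |
| Day 12 | study day 19 (Week 3 Day 5), after the course | study day 12 (Week 2 Day 5), last infusion day |
| Day 15 | study day 22 (Week 4 Day 1) | study day 15 (Week 3 Day 1) |
| Day 22 | study day 29 (Week 5 Day 1) | study day 22 (Week 4 Day 1) |

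**HACA under each count.** From priming, Days 8 and 12 bracket the course just as Days 1 and 5 do in Arm A. Under Table 6 the first sample falls 15 − 9 = 6 days after the first infusion and 15 − 12 = 3 days after the last. The second falls 19 − 12 = 7 days after the last. The calendar's ±2-day windows do not remove the problem: the earliest draw is 15 − 2 = 13 and the latest first infusion is 9 + 2 = 11.

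**Neither count fits every Arm B sheet.**
- Under Table 6, Cycle 2 Day 1 is 7 + 21 + 1 = study day 29. PK Cycle 1 Day 22 is then the same visit.
- Counted from priming, Cycle 1 Day 1 repeats the Priming Day 1 row on the PK, Luminex, CyTOF and banking sheets. The last three then have no draw on study day 22, although Table 2 asks for weekly Luminex and CyTOF draws in Cycles 1–2. Cycle 1 would also run to 28 days, against the stated 21.
- One of the 12 rows of the Arm B PK worksheet (Appendix H) is therefore redundant under either count.

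**Size.** Arm B maximum = 3 × 20 + 10 = 70. Neuroblastoma cohorts B1 and B2 = 2 × 20 = 40.

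**The case against.** The strongest reply is that the intended timing is clear. Appendix O ties the first sample to a point before dinutuximab and the second to the end of an infusion. Under the Table 6 count no dinutuximab is given near either day, so that reading makes the worksheet unworkable and cannot be the plan. Table 3 agrees. Its Cycle 1 row headings are cut off in this copy, but the order of the rows survives: the HACA tube before dinutuximab goes with the first of three weekly Cycle 1 draws, and the tube after dinutuximab comes before the second. Several other places also count from priming, so no single numbering can be called the protocol's own. Finally, HACA is exploratory, and Section 9 specifies no analysis of it.

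All of this stands, and it settles what was meant. It does not make the label safe. The Appendix O instruction does not say the first infusion, so at Week 3 Day 1 a site can satisfy it literally, because the next infusion is in Cycle 2. The Day 12 instruction would expose the mismatch, but only once the pre-dose window has closed. The Table 6 count is also the one the same coordinator uses for dosing and for the Luminex, CyTOF and banking sheets.

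**Conclusion.** The Arm B Cycle 1 labels are inconsistent and should be reconciled. Where a site applies the Table 6 count to the HACA row, the pre-dinutuximab sample moves to study day 15 and the only Arm B HACA baseline is lost. The day arithmetic uses nominal visit days and assumes no dose delay.

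A reader might go further and infer that Arm B has no HACA baseline by design, so that pre-existing and treatment-induced antibody cannot be separated in any of its patients. The documents do not support that. A pre-dose draw is intended, and it is obtained wherever the labels are counted from priming or the Appendix O instruction is taken to mean the first infusion.

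Seventy is the largest number exposed, reached only if all four cohorts fill and every site reads the label the Table 6 way. The documents give no basis for estimating how many sites would. The rationale in Section 2.3.1 concerns neuroblastoma patients, at most 40. No primary or secondary endpoint depends on HACA. The change is still worth making, because the sample is mandatory, cannot be replaced, and costs nothing to protect.

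**What to change.** Use one numbering for every Arm B sampling label: priming separate, and Cycle 1 Day 1 equal to Week 2 Day 1. Print the study week beside each time point.

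- **HACA (Table 2, Appendix O).** Relabel the Arm B samples as Cycle 1 Day 1 (Week 2 Day 1), before the first dinutuximab infusion, and Cycle 1 Day 5 (Week 2 Day 5), immediately after the dinutuximab infusion. This matches Arm A.
- **PK (Table 2, Appendix H).** In Table 2, replace the Arm B Cycle 1 entries with Priming Day 1 and Cycle 1 Days 1, 8 and 15. In Appendix H, delete the redundant Cycle 1 Day 22 row. Deleting Day 22 from Table 2 alone would be a mistake: Arm B has no Safety Lead-In, so that row would then hold no priming PK sample for Arm B.
- **FcR and KiR baseline (Table 2, Appendices K and M) and the C1D1 draw in Section 5.2.** Relabel these as Priming Day 1.
- **Section 8.1.1.** Reconcile its label for the priming dose with Table 6.

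If Arm B samples have already been taken, classify each as pre- or post-dinutuximab from the actual date and time recorded in Appendix O, not from the label.

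The cost is table and worksheet wording in an amendment. No extra samples are needed, and one redundant PK row goes.
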